Ketamine, given for postoperative pain control, can be hypothesized to have long lasting analgesic effects as well as effects on improving mood and function in the postoperative period. Ketamine can be administered as a single dose in the post-anesthetic care unit (PACU), where patients are closely monitored for potential side effects. We hypothesize that postoperative use of ketamine should lead to improvement in pain indices including visual analog scale (VAS), a decrease in opioid requirement, mood improvements as measured by psychometric indices, and finally improvements in functional measures including early mobility and faster discharge from the hospital. In addition, we will assess serum levels of IL-1, 6, TNF- α , and BDNF to see if alterations in levels of cytokines and neurotrophic factors occur with postoperative pain and how ketamine treatment may influence the levels of these biomarkers.

Study Objective

Specific aim 1: examine the effect of a single, subanesthetic dose (0.4mg/kg) of ketamine vs. saline control on mood and postoperative function in patients who have undergone gastric bypass and sleeve gastrectomies.

Pain relief and changes in postoperative mood and function will be assessed using both patient report, in the forms of a series of questionnaires, and medical chart review. The questionnaires we use will be Beck Depression Inventory (BDI), Visual Analog Scale (VAS), McGill's short form, QoR-15 form and the Montgomery-Asberg Depression Rating Scale (MADRS). Please see below for a detailed discussion of these forms. In addition, from the chart review we will monitor length of stay during hospitalization, opioid usage per hour during the PACU stay before and after ketamine infusion, total opioid usage per day throughout the hospital stay, time to out of bed to chair, and spirometry use after ketamine infusion.

Specific aim 2: examine the effect of a single, subanesthetic dose (0.4mg/kg) of ketamine vs. saline control on inflammatory cytokines and neurotrophic factors in the postoperative period.

We will examine the effect of ketamine on proinflammatory markers and neurotrophic factors known to be linked with pain. We will examine levels of interleukin factor 1 and 6 (IL-1, IL-6), TNF- α , and BDNF. This aim will provide potential mechanism of action for ketamine.

Overall study design and plan

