An additional component of the study, which is entirely optional, is to obtain patient serum samples (about two teaspoons) in the operating room and 15 minutes and 4 hours after ketamine infusion. We will use these samples to assess levels of IL-1, IL-6, TNF- α , and BDNF, which are markers for pain. In addition, with patient consent, we will also store serum samples for future research use to measure other cytokines and neurotrophic factors and molecular markers associated with pain and depression.

Study site: Tisch Hospital

Outcome measures

Primary outcome measure: scores on the following questionnaires: 1) The Beck Depression Inventory (BDI); 2) Visual Analog Scale (VAS) score; 3) McGill's short form; 4) QoR-15 form; and 5) Montgomery-Asberg Depression Rating Scale (MADRS). The BDI and MADRS provide assessments for mood and function, VAS and McGill's assess pain, and QoR-15 assesses patient's overall satisfaction with postoperative recovery.

After consent is achieved in the pre-admission clinic prior to surgery, patients will be asked to fill out BDI, MADRS and QoR-15 forms to establish baseline scores. The BDI, MADRS will be filled out on postoperative days (POD) 0 after the infusion of ketamine, and BDI, MADRS and QoR-15 forms will be repeated on POD1, 2 and 7. McGill's short form will be filled out prior to discharge from the PACU and on POD 1, 2 and 7. VAS will be filled prior to PACU discharge, and every day while patient is in the hospital and on POD 7. VAS is a routine part of hospital care and will be administered daily whether a patient is enrolled in the study or not. If a patient has been discharged prior to POD2 or 7 (patients typically are discharged on POD2 or 3 in our practice), then a member of the study team will contact the patient by telephone to fill out these questionnaires.

Secondary outcome measures: 1) length of stay during hospitalization; 2) opioid usage per hour during the PACU stay before and after ketamine infusion; 3) opioid usage per day throughout the hospital stay; 4) time to out of bed to chair (OOB); 5) spirometry use 4 hours after the termination of ketamine infusion; 5) anti-emetic use in the PACU.

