Sample Size Justification: Previous studies on the antidepressant effects of ketamine on depressed patients typically yield a mean difference in psychometric measures of 40%, with a standard deviation of roughly 40% as well. Power analysis yields $n = 50$ patients in each arm. This will allow for us to detect a true difference in the mean value of our outcome variable of $\pm 22.5\%$ with a probability (power) of 0.8. The type I error probability associated with this test of the null hypothesis that the population means of the ketamine versus control groups are equal is 0.05.

Statistical Analysis: For this study, descriptive statistics will be performed for all data and subgroups as needed:

- 1) Outcome tests (see above), N (%) for each category, showing absolute values, absolute

and percent differences, stratified by treatment etc.

- 2) Demographics showing continuous parameters (age, height, weight, etc.) as mean + SD; categorical parameters, as N (%); all also stratified by treatment.

Analysis of variance (ANOVA) test with repeated measures will be performed to determine within-patient effects (time) and between patient effects (treatment) on outcome measures. Pearson correlation will be used to assess relationships between continuous variables, and Spearman's Rho will be used for ranked data. For non-normally distributed, the Kruskal-Wallis test will be used for global significance, and Mann Whitney for subsequent pairwise comparisons.

Exploratory analysis will fit continuous (VAS score, length of stay in the hospital) and categorical (ordinal outcome data) to a Logistic Regression model which predicts the treatment bivariate (IV ketamine or placebo).

Interim Data analysis: An interim data analysis will be performed after a total of 50 patients have completed the study. An analysis of primary and secondary endpoints will be analyzed, and if the primary endpoints are met, we will opt to terminate the study.

DATA SAFETY AND MONITORING PLAN

Timeline

- 1) Estimated start date: Sept 1, 2013
- 2) Estimated time for start-up: 2 months
- 3) Time allotted for enrollment: 2 years
- 4) Estimated study end date: August 30, 2015

Data acquisition and management

The research material obtained from human subjects in this proposed study will be collected solely for research purposes. It will be as follows:

- a. *Clinical information* obtained by medical history, questionnaires and interviews.

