Sample Size Justification: Previous studies on the antidepressant effects of ketamine on depressed patients typically yield a mean difference in psychometric measures of 40%, with a standard deviation of roughly 40% as well. Power analysis yields $n = 50$ patients in each arm. This will allow for us to detect a true difference in the mean value of our outcome variable of $\pm 22.5\%$ with a probability (power) of 0.8. The type I error probability associated with this test of the null hypothesis that the population means of the ketamine versus control groups are equal is 0.05.

Statistical Analysis

For this study, descriptive statistics will be performed for all data and subgroups as needed:

- 1) Outcome tests (see above), N (%) for each category, showing absolute values, absolute and percent differences, stratified by treatment etc.
- 2) Demographics showing continuous parameters (age, height, weight, etc.) as mean + SD; categorical parameters, as N (%); all also stratified by treatment.

Analysis of variance (ANOVA) test with repeated measures will be performed to determine within-patient effects (time) and between patient effects (treatment) on outcome measures. Pearson correlation will be used to assess relationships between continuous variables, and Spearman's Rho will be used for ranked data. For non-normally distributed data, the Kruskal-Wallis test will be used for global significance and Mann Whitney for subsequent pairwise comparisons.

Exploratory analysis will fit continuous (VAS score, length of stay in the hospital) and categorical (ordinal outcome data) to a Logistic Regression model which predicts the treatment bivariate (IV ketamine or placebo).

Interim Data analysis

An interim data analysis will be performed after a total of 50 patients have completed the study.

An analysis of primary and secondary endpoints will be analyzed, and if the primary endpoints are met, we will opt to terminate the study.

Data Safety and Monitoring Board (DSMB)

In addition to the PI, [name], an independent patient safety DSMB panel will also review study documents and safety data on a routine basis. This board will meet once every three months, and more frequently as needed. In addition, the board will meet with study coordinator and assistant after a total of 50 patients have completed the study to perform an interim analysis. This board will include the additional following members from the department of anesthesiology.

1. [name]
2. [name]

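### The stop-for-success look at 50 of 100 patients defines neither success nor a significance level at either look, so the stated 0.05 is not protected

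*Combined protocol and SAP*

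**What the plan says.** The rule appears twice in the same words, in the Interim Data analysis paragraph under Statistical Analysis and again in the Data Safety and Monitoring Plan: "An interim data analysis will be performed after a total of 50 patients have completed the study". It continues: "An analysis of primary and secondary endpoints will be analyzed, and if the primary endpoints are met, we will opt to terminate the study". The DSMB paragraph adds that "the board will meet with study coordinator and assistant after a total of 50 patients have completed the study to perform an interim analysis", but gives the board no criterion.

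Four other places bear on how the rule would be applied:

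- Outcome measures: "Primary outcome measure: scores on the following questionnaires: 1) The Beck Depression Inventory (BDI); 2) Visual Analog Scale (VAS) score". The list goes on to McGill's short form, QoR-15 and MADRS, with no rule for combining the five. Each is scheduled on several days; for example, "BDI, MADRS and QoR-15 forms will be repeated on POD1, 2 and 7".
- Statistical Analysis: a repeated-measures ANOVA is planned to "determine within-patient effects (time) and between patient effects (treatment) on outcome measures". No time point or contrast is named as decisive.
- Sample Size Justification: a difference of ±22.5% in one outcome variable, SD roughly 40%, 50 per arm, power 0.8. The type I error for the test that the "population means of the ketamine versus control groups are equal is 0.05" is the only error rate in the document.
- Study Rationale: "We hypothesize that postoperative use of ketamine should lead to improvement in pain indices". This gives a direction for the hypothesis but is not tied to the stopping rule.

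**The concern.** Four things are needed to apply the rule, and none is stated:

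1. Which endpoints must succeed. The plural suggests all five, but the plan does not say so.
2. Which visit or contrast counts on each.
3. What success means, in direction and in p-value.
4. The levels: there is no interim boundary and no adjusted final level.

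Testing the same endpoint at half and at full sample gives two chances of a false positive. If each look uses the full 0.05, the overall error can exceed 0.05. By how much depends on the reading, and nothing fixes the reading before the interim data are seen. A trial that stops early on a significant result also tends to report an effect larger than the true one.

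**Working it through.** **Inputs from the documents.** SD 40%; difference 22.5%; two-sided 0.05; 50 per arm; 1:1 allocation; interim at 50 of 100 patients (25 per arm, information fraction 0.5).

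**Assumptions.** p<0.05 at both looks, because 0.05 is the only level given; a two-group comparison of means in the normal approximation (the planned repeated-measures ANOVA could differ); and a common correlation between the five scores, scanned from 0 upward because the documents give none.

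**1. The plan's own figure.** n per arm = 2 × (1.960 + 0.842)² × (40/22.5)² = 2 × 7.85 × 3.16 = 49.6, so 50. At 50 per arm the standard error is 40 × √(2/50) = 8.0, and power is Φ(22.5/8.0 − 1.960) = Φ(0.853) = 0.803 (0.795 with the t distribution). The stated figure reproduces as a two-sided, single-look calculation. It makes no allowance for an interim test.

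**2. One deciding endpoint, no true effect.** Let Z1 and Z2 be the statistics at the two looks, with correlation √0.5 = 0.707.

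- Stop on significance in either direction: 1 − P(|Z1|<1.96, |Z2|<1.96) = 0.083. A t-test simulation with 25 and then 50 per arm also gives 0.083.
- Stop only when ketamine is favoured, with a two-sided final test: 1 − P(Z1<1.96, |Z2|<1.96) = 0.067. False claims for ketamine make up 0.042 of this, against 0.025 with one look.

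**3. Five endpoints, no true effect on any** (simulation):

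| Reading | Quantity | Ketamine-favouring stop | Either direction |
|---|---|---|---|
| Any one suffices to stop | error of each endpoint | 0.063 to 0.065 | 0.076 to 0.077 |
| Any one suffices to stop | at least one false positive | 0.19 to 0.29 | 0.23 to 0.35 |
| All five needed to stop | error of each endpoint | 0.050 to 0.052 | 0.050 to 0.055 |

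The any-one rows cover correlations from 0 to 0.7, and the all-five row from 0 to 0.8. With a single final look, the chance of at least one false positive is already 0.15 to 0.23. Most of the second row is therefore endpoint multiplicity, not the interim look.

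**4. All five needed to stop, four truly improved by 22.5%.** The fifth, unaffected endpoint has error 0.051 at correlation 0 and 0.066 at correlation 0.7.

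**5. The estimate after an early stop (one endpoint, p<0.05).** The interim standard error is 40 × √(2/25) = 11.3, so stopping needs an observed difference of 1.96 × 11.3 = 22.2%. With a = 1.96 − δ/11.3 for a true difference δ, the mean estimate among stopped trials is δ + 11.3 × φ(a)/(1 − Φ(a)).

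- True 22.5%: 51% of trials stop, with a mean estimate of 31.3%.
- True 40%: 94% stop, with a mean estimate of 41.4%.

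**6. With O'Brien-Fleming levels (0.005, then 0.048).** The error for one endpoint is 0.0499 for an either-direction stop and 0.0490 for a ketamine-favouring stop, of which 0.0250 favours ketamine. Power at a true 22.5% is 0.800.

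**The case against.** The strongest reply is that the plan never says the interim is tested at p<0.05, and that its most literal reading, all five endpoints, gives almost no inflation when ketamine affects none of them. The 0.083 needs two departures from that reading: a single deciding endpoint, and a placebo-favouring result counted as success. If all five were also required for final success, the chance of a false claim on all five would be below 0.01 at correlations up to 0.8 with no effect on any score. The 0.050 to 0.083 range also assumes no true effects. Under the any-one rule with a ketamine-favouring stop and four endpoints truly at 22.5%, the unaffected endpoint's own error is about 0.045 to 0.051. The larger any-of-five figures mainly reflect multiplicity. Finally, a DSMB reviews the interim, and protocol changes need IRB approval.

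Much of this stands. The plan cannot be said to exceed 0.05 under every reading, and the multiplicity figures should not be charged to the interim look. But the all-five reading is not written down. Even under it, with four endpoints truly affected, an unaffected fifth can have error up to 0.066. If all five are also required for final success, the chance of a false claim can reach about 0.04, against 0.025 at a single look. The DSMB and IRB are partial safeguards, but neither supplies a boundary.

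**Conclusion.** The concern holds. The plan contains an efficacy stopping rule that cannot be applied without choices it does not make, and those choices decide whether the stated 0.05 is kept. With p<0.05 at both looks and no true effects, the error per endpoint runs from 0.050 (all five needed to stop, low to moderate correlation) through 0.067 (one endpoint, ketamine-favouring stop) to 0.083 (one endpoint, either direction). The defect is that 0.05 is not guaranteed, not that it is always exceeded. Overestimation after an early stop is material at a true 22.5% and small at 40%. The interim threshold and the correlations are assumptions. The missing definitions and levels are plain in the text. The rule must be settled before the interim data are seen, because a boundary chosen afterwards would not be credible.

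**What to change.** Amend both Interim Data analysis paragraphs identically, before any interim data are seen:

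1. Name the endpoint that drives stopping, with its visit or repeated-measures treatment contrast. Otherwise state that all five are required, and give the contrast for each.
2. Define success as a result favouring ketamine that crosses a pre-specified two-sided boundary, and say that a placebo-favouring result does not count. O'Brien-Fleming p<0.005 at 50 patients and p<0.048 at 100 is one option; any other pre-specified pair that holds 0.05 would also do.
3. If any one of the five may suffice, make the boundaries cover the five endpoints as well.
4. State that an estimate from an early stop is likely to be too large and will be reported with that caution.

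Alternatively, make the 50-patient look safety-only and keep 0.05 at the end. That costs no power but gives up stopping for success.

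The main cost is a design decision on what drives stopping; after that it is one paragraph in two places, with 100 patients unchanged. At a true 22.5%:

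- **One endpoint:** power is 0.800 against 0.803 with a single look, and the chance of early stopping falls from 51% to 21%. Trials that do stop overestimate more (mean 38% against 31%), because p<0.005 needs an observed difference of about 31.8%.
- **All five required:** the chance of stopping is 0.04% to 5.5%, and power for all five is 0.32 to 0.59, against 0.33 to 0.60 with a single look (correlation 0 to 0.7).
- **Any of five, Bonferroni at 0.01 each:** O'Brien-Fleming needs p<0.00026 and then p<0.0099, with power per endpoint of about 0.59.

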This is a randomized, double-blind, placebo-controlled, two-arm parallel, single-center study. One hundred subjects (50 in each arm) will be enrolled. Subjects, between the ages 18 and 65, undergoing laparoscopic gastric bypass or sleeve gastrectomy under general anesthesia will be screened for eligibility to participate in the study. Subjects will be screened, recruited and consented during the preadmission visit prior to surgery. Eligible subjects will be randomized to one of the two treatment group in a 1:1 ratio to receive either IV ketamine (0.4mg/kg) or matching placebo. Both men and women will be recruited, and there is no limitation as to racial and ethnic origin.

Participation in the study will not alter the patient's surgical or anesthetic care, post-anesthetic care, or care on the floor. In the PACU, patients, if deemed medically stable by the study physician, will receive either 0.4mg/kg IV ketamine or placebo. All patients will also receive standard post-anesthetic monitoring and care, as well as routine care after transfer out of the PACU. There is no restriction on the use of other analgesics throughout the hospital stay. Patients are followed until the date of discharge, and endpoints (see below) are collected from patient reports as well as from medical charts. During their hospital stay (and once after their discharge from the hospital), patients will fill out five questionnaires which provide estimates of their postoperative pain control, mood and function, and quality of postsurgical recovery.

Patients will be randomized using a block randomization code for assigning 100 subjects to two groups. In Excel we generated 100 random numbers. In the next column we inserted multiple copies of the sequence PCPC where p= "placebo" and c = "control", forming 25 blocks. Then we sorted the random numbers in each 4 subject block, including the assignment letters (P, C) in the sort. The remaining list of Ps and Cs is the randomization.

To check the balance, we then did running counts of the cumulative repeats of "p" and "c" and "p - c". The tally for each totaled 50 and the two groups were always within 2 counts of being perfectly balanced, which met our goal. The list can be extended at will to accommodate screening failures.

Randomization lists will be sent to the pharmacy who will then be able to distribute the study drug/placebo as patients are enrolled and undergoing surgery, and the remainder of the study staff will be blinded.

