- b. *Clinical information* obtained from chart review of the subjects' hospital records
- c. *Serum samples* will be obtained.

All research data will be collected in Case Report Forms (CRFs). Clinical safety data, routine labs, screening information, informed consent, and progress notes will also be collected in Source Documents.

Data Entry: CRFs of all research data will be entered into assessment specific data entry forms with macro programming to organize repeated measures into table format. Data and results from laboratory tests will be entered by study staff directly from the CRFs into secure computer designated for [name] at NYU-Tisch Hospital. The data are then stored using a secure password. The computer used for this study will be password protected and kept locked in a locked office in the Anesthesia office. Only designated study staff will have access to patient data and these include: the PI of the study [name], the Research Coordinator and the Research

Assistant. Hard paper copies of the laboratory results, if necessary, will be stored in a secured area in [name] office in Alexandria Center for Life Sciences. Though the information collected in this study may be published, no patient will be identified by name or other personal information.

Adverse events will include events reported by the subject and thought to be associated with the research. Unanticipated problems and adverse events will be gathered by study investigators. Adverse events will be evaluated throughout the hospital stay. Any serious adverse effects will be reported to the IRB according to regulatory requirements.

Quality Assurance: Source Documentation and CRF's collected for the first 5 participants will be reviewed by the PI, [name], following completion of testing with each participant. Study procedure consistency, data entry accuracy and completeness, and normative range of values will be checked. Where applicable, consistency between Source Document and CRF will be evaluated. Thereafter, source documentation and CRF's for 1 out of every 5 participants will be selected randomly and reviewed in a similar manner. If an error or errors are discovered, corrective action will be taken to remedy particular errors when discovered.

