None of these DSMB panel members has any conflict of interest with this study protocol.

Study safety assurance

Confidentiality and Study Assessments: To safeguard against the loss of confidentiality, all information will be stored on locked files which can be accessed only by members of the research staff for this project. No names or other identifying information will be used in publications which stem from this research. Subjects will be informed of these exceptions in the informed consent document.

Reporting of Adverse Events (AEs): The DSMB Panel will report a study summary and updates on the clinical safety documentation and assessments, as well as the primary outcome measures. Baseline demographics, recruitment rates and reasons of ineligibility, as well as study retention rates, will be summarized. An update of regulatory status and any protocol amendments will be provided. A summary of adverse events (AEs) and serious adverse events (SAEs) that have occurred will be provided.

An AE is defined as any reaction, side effect, or untoward event that occurs during the course of the clinical trial, whether or not the event is considered medication-related or clinically significant. A new illness, symptom, sign, or worsening of a pre-existing condition or abnormality is considered an AE. Stable chronic conditions, such as arthritis, which are present (and documented) prior to clinical trial entry and do not worsen are not considered AEs. AEs will be recorded on the AE Form. The AE Form is also used to record follow-up information for unresolved events. Each month, a study investigator and/or study clinician (physician, nurse, or physician's assistant) will review the AE Form completed for the previous month for any events that were reported as continuing, and provide corrective action as needed. Per the IRB of the NYUSOM policies, only those adverse events that are unexpected and related to the study drug, and those events that are harmful, will be submitted to the IRB within five days. All other events will be reviewed by the DSMB.

All adverse events will be collected – whether they are related to study drug or not, and submitted to the IRB or not. Events will be collected by speaking to the patients as well as through the medical record. Data will be kept up to date by patient, and investigator will be notified when something comes up.

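### The plan gives two incompatible rules for which adverse events are collected and when, and sets no end day; if the hospital-stay rule governs, the safety window ends at discharge, so its length equals a trial outcome.

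*Combined protocol and SAP*

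**What the plan says.** The combined protocol and SAP describes adverse-event collection in several places.

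- **Data acquisition and management.** Scope: "Adverse events will include events reported by the subject and thought to be associated with the research". Timing: "Adverse events will be evaluated throughout the hospital stay".
- **Reporting of Adverse Events (AEs).** An adverse event is "any reaction, side effect, or untoward event that occurs during the course of the clinical trial, whether or not the event is considered medication-related". All events are to be collected, "whether they are related to study drug or not, and submitted to the IRB or not". On sources: "Events will be collected by speaking to the patients as well as through the medical record". No time points are given.
- **Reporting of Serious Adverse Events (SAE).** Any serious event from any cause during the investigation is reportable, related or not.
- **Overall study design and plan.** "Patients are followed until the date of discharge", although the same paragraph also has patients complete questionnaires once after leaving hospital.
- **Outcome measures.** Questionnaires run to POD7, and usual discharge is POD2 or POD3. For patients already at home, "then a member of the study team will contact the patient by telephone to fill out these questionnaires". Adverse events are not mentioned for that call.

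Length of stay is the first secondary outcome, and Study Rationale hypothesises earlier discharge on ketamine.

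**The concern.** The two descriptions differ in three ways: source (subject report, or patient plus medical record), relatedness (thought related, or all events) and period (hospital stay, or course of the trial). Staff cannot follow both. The data-management text sits beside the CRF instructions and is the only text that says when adverse events are evaluated. The broader definition has no end day and no post-discharge step, so it does not settle the period by itself.

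Two things are at stake. First, benefit would be assessed to POD7 while harm might be assessed only to discharge. A readmission on POD5 would count as serious under the plan's own definition, yet no scheduled step after discharge asks about it. Second, a window that closes at discharge has the same length as the hospital stay, which the treatment is expected to shorten. Randomisation and blinding do not protect an adverse-event summary against unequal observation time that arises after treatment.

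**Working it through.** **No plan figure to reproduce.** The plan states no adverse-event rate, no collection end day and no adverse-event comparison between arms. Its sample size of 50 per arm does not enter this point and is unaffected by it.

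**Inputs.** Usual discharge on POD2 or POD3 and last scheduled assessment on POD7 (Outcome measures); shorter stay hypothesised on ketamine (Study Rationale).

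**Step 1: share of follow-up left uncovered if collection stops at discharge.** This depends on how days are counted.

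| Discharge | Calendar days covered, of 8 (POD0–7) | Uncovered | Elapsed days covered, of 7 | Uncovered |
|---|---|---|---|---|
| POD2 | 3/8 = 37.5% | 62.5% | 2/7 = 29% | 71% |
| POD3 | 4/8 = 50% | 50% | 3/7 = 43% | 57% |

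If the all-events, whole-trial wording governs, these shares do not apply as they stand. What remains is that no end day or post-discharge query is specified.

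**Step 2: difference in window if one arm left on POD2 and the other on POD3.** Calendar days: 1 − 3/4 = 25% shorter. Elapsed days: 1 − 2/3 = 33% shorter. The one-day difference is an assumption, since the plan gives no expected size for the effect on stay.

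**Step 3: what an unequal window could do to a summary by arm.** The plan gives no event rate, so assume a true 7-day risk p of 10%, 20% or 40%, identical in both arms, with constant hazard. The risk captured by day t is 1 − (1 − p)^(t/7).

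| p | Captured by POD2 | By POD2.5 | By POD3 | Ratio, POD2 vs POD3 | Ratio, POD2.5 vs POD3 |
|---|---|---|---|---|---|
| 10% | 2.97% | 3.69% | 4.42% | 0.67 | 0.84 |
| 20% | 6.18% | 7.66% | 9.12% | 0.68 | 0.84 |
| 40% | 13.58% | 16.68% | 19.66% | 0.69 | 0.85 |

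For example, at p = 20%: 1 − 0.8^(2/7) = 6.18%, 1 − 0.8^(3/7) = 9.12%, and 6.18/9.12 = 0.68, with no true difference between arms.

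**Step 4: the opposite limit.** If every event arose before the earlier discharge, both windows would capture all of them and the ratio would be 1.00. It is also 1.00 under equal risks when both arms are observed to POD7. The ratios in Step 3 therefore show how the mechanism works; they do not predict this trial's result.

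**The case against.** The strongest reply is that the dedicated safety sections already state the right rule. They collect all events, related or not, from patients and records. They provide an AE Form with monthly review of continuing events, which is not tied to discharge, and they require any-cause serious events to be reported. The data-management wording is not expressly exclusive either: it says what adverse events include and that they are evaluated during the stay. This stands in part. On relatedness, the plan already contains the rule it needs, and the task is to remove the competing text. On timing, the reply falls short, because no section names an end day or a query after discharge.

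Three stronger readings are tempting, and the documents do not support them.

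- **The plan restricts collection to related, in-hospital events.** A reader might infer this from the data-management section, where restriction is the natural reading. But the word *only* is not there, and two other sections say otherwise. The uncovered shares are therefore conditional.
- **Adverse-event counts will favour ketamine.** The effect on stay is a hypothesis with no stated size. Intervention Administration expects most side effects to clear soon after the infusion, the pharmacology section gives 30–45 minutes for injected effects, and the risk/benefit text describes the main risks as short-lived. Constant hazard is thus a poor model for acute drug effects. The Statistical Analysis section specifies no adverse-event comparison; the reporting section promises only a summary.
- **Flashbacks and other psychiatric effects will be missed.** These are listed as general ketamine effects, with nothing to say that they arise after discharge following a single low dose. If reported, they would count under the broad definition.

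**Conclusion.** The concern holds as an inconsistency that should be corrected. The sections disagree on source, relatedness and period, and none fixes an end day or asks about adverse events after discharge.

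Its size depends on which text governs. Under the hospital-stay rule, with discharge on POD2 or POD3, half or more of the period to POD7 goes unobserved on either day count. Bias between arms is possible but not shown. It needs a real difference in length of stay, and events that continue to arise after the acute phase. Acute effects should fall inside either window, and serious events are less exposed because their reporting rule covers the whole investigation. The primary efficacy analysis and the sample size are not affected.

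**What to change.** Reconcile Overall study design and plan, Data acquisition and management, and the AE and SAE reporting sections so that they state one rule:

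1. Use the all-events definition from Reporting of Adverse Events (AEs) throughout, and delete the relatedness and hospital-stay wording under Data acquisition and management.
2. Set one collection window for every patient, from infusion to the existing POD7 contact, regardless of discharge day. State follow-up to POD7 in the design section.
3. Add one open adverse-event question to the POD7 contact, asked of every patient whether at home or still in hospital.
4. Summarise adverse events by arm over this window, with the number of patients reached on POD7 in each arm.

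The cost is one question and one CRF line, plus the work of classifying and reporting any events found. No extra visit or patient is needed. Ending at POD7 is a practical choice, because that contact already exists. What matters statistically is that the end point is fixed and the same in both arms.
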